3. SAMPLE SIZE DETERMINATION

All sample size calculations were done at the time of protocol design and in preparation for the primary analysis. No update of the sample size and/or power calculations have been done.

3.1. Efficacy (Total Sample Size)

[figure not shown]
The study TNE is determined using the following assumptions:

1. a VE for molecularly confirmed, moderate to severe/critical SARS-CoV-2 infection of 60%.
2. approximately 90% power to reject a null hypothesis of $H_0: VE \leq 30\%$.
3. type 1 error rate $\alpha = 2.5\%$ to evaluate VE of the vaccine regimen (employing the sequential probability ratio test [SPRT] to perform a fully sequential design analysis; detailed in Section 5.4.3.1).
4. a randomization ratio of 1:1 for active versus placebo

Events for the co-primary endpoints are defined as first occurrence of molecularly confirmed, moderate to severe/critical COVID-19 according to the case definition in Section 5.2 in the PP population at least 14 days after double-blind vaccination (Day 15) and at least 28 days after double-blind vaccination (Day 29) with study vaccine.

Under the assumptions above, the total TNE to compare the active vaccine versus placebo equals 154, based on events in the active vaccination and placebo groups, according to the primary endpoint case definition of moderate to severe/critical COVID-19 (Section 5.2). Using the SPRT until the TNE when starting from the 20th endpoint onwards will result in 86.22% power to reject H_0 when $VE_1 = 60\%$. The overall type I error is controlled below 2.5% at 2.398% when $VE_0 = 30\%$. In Figure 3 the power of the testing strategy for VE_1 equal to 60%, 65%, 70% and 90% is shown for a total number of endpoints from 20 to 154. From the graph, the overall study power equals 96.6% for an assumed $VE = 65\%$, and close to 100% for an assumed $VE = 70\%$.

Figure 3 Theoretical Power based on the Exact Binomial distribution for $VE1 = 60\%, 65\%, 70\%$ and 90% ; and Type I error rate under $VE0 = 30\%$

If the primary hypotheses testing is successful, secondary objectives will be evaluated against a null hypothesis employing a lower limit $VE > 0\%$. The method to perform hypothesis testing of primary and secondary objectives preserving the FWER is specified in section 2. The FWER will be controlled at 2.5%.

Sample Size Justification

Based on epidemiological modeling for the targeted study countries, province/states of the various site locations, the annualized incidence of moderate to severe/critical COVID-19 cases meeting the primary endpoint definitions has been predicted to be 1.4% for the October-November timeframe. The estimate incorporates that real-world-evidence data and literature data only detected and reported a fraction of SARS-CoV-2 infections.

Furthermore, it includes that, based on literature and real-world-evidence data, only a fraction of all infections meets the moderate to severe/critical COVID-19 case definition and the fraction varies by age as well (increasing with higher ages). Moreover, projections for the selected study regions indicate that incidences will decline over time. Finally, seroprevalence rates are expected to vary between 5-15%.

For the purpose of sample size evaluation, an incidence assumption of moderate to severe/critical COVID-19 cases meeting the primary endpoint definition of 1.4% during the first 3 months of the

study, with a 50% reduction in Month 4, and 62% reduction in the months thereafter is assumed in combination with a seroprevalence rate of 10%.

The epidemiological situation will remain uncertain during the course of the study: actual seroprevalence rates, degree of social distancing and use of personal protective equipment during the study, local regulations (eg, potential lockdowns, other vaccines if available) potentially becoming in effect during the course of the study and potential drop-outs from the study may impact the disease incidence rate.

To that end, the maximum sample size of approximately 60,000 participants will be selected. This sample size is selected, based on the uncertainty of the epidemiological situation in combination with the ability to provide a high probability (approximately 90%) to reach a time to signal within 8 months of the study for a vaccine with an assumed 60% VE.

Based on an estimated case-hospitalization ratio of 2.5% and estimates obtained from reported real-world-evidence data of 3-10% of all SARS-CoV-2 infections meeting the severe/critical COVID-19 definition, this will provide a reasonable likelihood of observing 5 severe cases in the placebo group within the same time frame (8 months).

Added in Protocol Amendment 3: The incidence of moderate to severe/critical COVID-19 seen in the US and reported in other COVID-19 vaccine trials is significantly higher than assumed at the time of protocol planning. Epidemiological model-predictions indicate a range of 3.8% to 6.3% for Nov 2020 and 4.1% - 6.3% for Dec 2020. Furthermore, the ratio of non-severe versus severe events has been reported approximately 5:1 to 17:1 in other COVID-19 vaccine trials (Nov 2020). Employing these assumptions, modeling indicated there is a high probability that a signal of efficacy meeting the prespecified criteria in the Protocol Amendment 3 could be reached at or prior to the time when 50% of the participants will have been followed for a 8 weeks from the time of immunization, and therefore the sample size was reduced from 60,000 to approximately 40,000 participants.

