2. STATISTICAL HYPOTHESES

The co-primary endpoints will evaluate

- the first occurrence of molecularly confirmed, moderate to severe/critical COVID-19 according to the case definition (Section 8.1.3.1 in the CTP), with onset at least 14 days post double-blind vaccination with Ad26.COV2.S or placebo, in the Per Protocol (per protocol (PP) population (see Section 4), including all events from both age groups, with and without comorbidities.
- the first occurrence of molecularly confirmed, moderate to severe/critical COVID-19 according to the case definition (Section 8.1.3.1 in the CTP), with onset at least 28 days post double-blind vaccination with Ad26.COV2.S or placebo, in the Per Protocol (per protocol (PP) population (see Section 4), including all events from both age groups, with and without comorbidities.

A successful primary efficacy conclusion will require:

1. Establishing the hypothesis $H_1: VE > 30\%$ for each co-primary endpoint with a VE point estimate $\geq 50\%$). The study is designed to test the co-primary hypotheses of vaccine efficacy (VE) in the PP population. For both co-primary endpoints the following hypothesis will be tested: $H_0: VE \leq 30\%$ versus $H_1: VE > 30\%$ and each hypothesis will be evaluated at a 2.5% one-sided significance level.

AND

2. A favorable split vaccine:placebo for the subset of primary endpoints meeting the severe/critical COVID-19 case definition (expressed as a VE point estimate against severe/critical COVID-19 molecularly confirmed endpoints $\geq 50\%$) and a minimum of 5 events in the placebo group. This requirement needs to be met separately for severe/critical events with start at least 14 days after double-blind vaccination and for severe/critical events with start at least 28 days after double-blind vaccination.

Both conditions 1. and 2. will simultaneously have to be met for both co-primary endpoints at the same calendar timepoint.

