5.4.3. Analysis Methods for double blind phase

Vaccine efficacy and evaluation of the primary hypotheses will be done based on the truncated sequential probability ratio test (Section 5.4.3.1) in the per-protocol analysis set including seronegative subjects.

The pre-specified boundary to declare a significant result for each of the co-primary endpoints is based on a one-sided truncated SPRT, assuming approximately 90% power to detect a VE=60%, at a 2.5% one-sided significance, starting from the 20th COVID-19 case in the PP population that meets the primary endpoint definition, up and until the 154th case (value at which the testing is curtailed). The boundary is visualized in Figure 6 .

In case interim monitoring has started (i.e. because minimal data requirements 1-3 were met) and the total number of events at the time of the primary analysis exceeds the TNE, e.g. due to rapid accrual of events in the last week, the SPRT boundary will be extended until the observed total number of events, keeping the overall alpha below 2.5% one-sided. This is achieved by avoiding the truncation of the SPRT boundary at the TNE, distributing the remaining alpha across the overrun events, in such a way as to maximize the boundary at the observed total number of events.

The operational evaluation of this boundary is detailed later in this section. As soon as this prespecified boundary has been crossed for both co-primary endpoints together with the second efficacy criterion related to the severe infections (simultaneously at the same calendar timepoint) and the other data requirements have been met, the primary hypotheses of vaccine efficacy (VE) against moderate to severe infections in the PP set: $H_0: \text{VE} \leq 30\%$ versus $H_1: \text{VE} > 30\%$ will be established.

To evaluate whether the second efficacy criterion has been met, the VE against severe infections will be calculated, as soon as the primary endpoints contain a subset of 5 severe events for each of the co-primary endpoints. If the point estimate $VE \geq 50\%$ AND a minimum of 5 cases observed in the placebo group for both co-primary endpoints, this criterion is considered to be met.

The analysis of the primary endpoint will evaluate vaccine efficacy and the associated 100% (1- $2\alpha^*$) - confidence interval with α^* as indicated in section 2 will be estimated as referenced in Appendix 8.

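### The 96.6% that section 3.1 calls overall study power is single-endpoint SPRT power; it leaves out the section 2 success rule, above all the severe-disease criterion

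*SAP*

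**What the plan says.** Section 3.1 sets the target number of events (TNE) at 154 from "a VE for molecularly confirmed, moderate to severe/critical SARS-CoV-2 infection of 60"%, "approximately 90% power to reject a null hypothesis of" VE ≤ 30%, one-sided alpha 2.5% and "a randomization ratio of 1:1 for active versus placebo". It then gives 86.22% power to reject at VE 60% for the SPRT started at event 20, with type I error 2.398%. It continues: "From the graph, the overall study power equals 96.6% for an assumed" VE of 65%, and nearly 100% for 70%.

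Section 2 defines primary success by two conditions. Condition 1 is rejection of VE ≤ 30% for each co-primary endpoint ("each hypothesis will be evaluated at a 2.5% one-sided significance level") with a point estimate of at least 50%. Condition 2 is a severe/critical VE point estimate of at least 50% with at least 5 placebo events, separately for onset from Day 15 and from Day 29. It adds: "Both conditions 1. and 2. will simultaneously have to be met for both co-primary endpoints at the same calendar timepoint".

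Section 5.4.3 describes the truncated SPRT boundary as "assuming approximately 90% power to detect a VE=60"%, and section 2 uses similar wording. On severity, section 3.1 reports that "the ratio of non-severe versus severe events has been reported approximately 5:1 to 17:1 in other COVID-19 vaccine trials". No section gives a power for the full rule.

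**The concern.** A reader takes *overall study power* to mean the probability that the study reaches its primary conclusion. Under section 2 that conclusion needs more than one boundary crossing. In particular, it needs a point-estimate hurdle on the small subset of severe cases, and such a hurdle can fail by chance when the vaccine performs exactly as assumed. If the stated figures omit it, the SAP credits the design with a power it does not have and understates the risk of a formally unsuccessful primary analysis. Attaching about 90% to the truncated SPRT adds to this, because section 3.1 itself gives 86.22% for that test.

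**Working it through.** **Inputs.** VE 60/65/70%, null VE 30%, 1:1 allocation, TNE 154 (section 3.1); the efficacy boundary of section 5.9.5 and Appendix 8; the success rule (section 2); monitoring from 42 Day-29 events (section 5.4.1). Severe share of moderate-to-severe events: 20/(60 + 20) = 25% from section 3.5.3; 1/(5 + 1) = 1/6 and 1/(17 + 1) = 1/18 from the ratios in section 3.1.

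**Step 1: reproduce the stated figures.** Each event falls in the vaccine arm with probability π = (1 − VE)/(2 − VE): 0.7/1.7 = 0.412 at VE 30%, 0.4/1.4 = 0.286 at 60%, 0.35/1.35 = 0.259 at 65%, 0.3/1.3 = 0.231 at 70%. An exact recursion over the boundary for one endpoint, events 20 to 154, gives:

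| True VE | Stated | Recomputed |
|---|---|---|
| 30% (type I error) | 2.398% | 2.398% |
| 60% | 86.22% | 86.22% |
| 65% | 96.6% | 96.61% |
| 70% | nearly 100% | 99.6% |

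The match is obtained with no second endpoint and no severe criterion in the calculation. Starting at event 42 gives 86.17% at VE 60%.

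**Step 2: where about 90% belongs.** A single fixed test at 154 events that rejects with at most 51 vaccine cases has type I error P(X ≤ 51 | 154, 0.412) = 2.46% and power P(X ≤ 51 | 154, 0.286) = 90.8%. That test sets the TNE. The truncated SPRT has 86.2%.

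**Step 3: what condition 1 adds.** The final boundary point has 49 vaccine and 154 − 49 = 105 placebo cases, so VE = 1 − 49/105 = 53.3%. This is the lowest VE on the boundary, so the 50% point-estimate requirement costs nothing up to 154 events. Requiring both nested endpoints gives 0.847 to 0.859 at VE 60%, a loss of about 1 to 2 points.

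**Step 4: why condition 2 bites.** With severe VE equal to overall VE of 60%, expected placebo severe events at 154 are 154 × share/1.4:

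| Severe share | Placebo severe | Vaccine severe (× 0.4) | Half of placebo |
|---|---|---|---|
| 25% | 27.5 | 11.0 | 13.8 |
| 1/6 | 18.3 | 7.3 | 9.2 |
| 1/18 | 6.1 | 2.4 | 3.1 |

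Vaccine severe events may not exceed half of placebo severe events, so the margin is narrow. At 1/18 the minimum of 5 placebo events is also at risk: about 26% of simulated trials have too few at 154 Day-29 events.

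**Step 5: the full rule by simulation.** Events are allocated to arm, severity and onset window, and all conditions are checked at each look up to 154 Day-29 events. Not in the SAP and therefore assumed: 80% of Day-15 events are also Day-29 events, 30% of events occur at age ≥ 60, and the Day-15 bound beyond 154 keeps the nominal alpha of the last look (0.0106). Varying the window split from 60% to 90% moves results by about two points.

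| Overall VE | Severe VE | 25% | 1/6 | 1/18 | Stated |
|---|---|---|---|---|---|
| 60% | 60% | 0.76 | 0.73 | 0.52 | 86.22% |
| 65% | 65% | 0.90 | 0.88 | 0.64 | 96.6% |
| 70% | 70% | 0.97 | 0.95 | 0.71 | nearly 100% |
| 60% | 80% | 0.85 | 0.84 | 0.61 | 86.22% |

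**Step 6: delayed analysis.** Section 5.4.1 allows one later analysis at the full 2.5% if 154 is passed before the data conditions are met. At share 1/18 with overall and severe VE both 60%, the probability becomes 0.53 if the condition is 5 severe cases in total (section 5.4.1), or 0.61 if it is 5 in the placebo group (section 5.9.5). With severe VE 80%, these become 0.66 and 0.80.

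**The case against.** No number in section 3.1 is miscalculated. The 86.22% is labelled as power to reject the null, the Figure 3 title refers to theoretical binomial power, and *overall* could mean cumulative over looks, as it does for the type I error in the same paragraph. The 90% in section 3.1 is a legitimate input to the TNE, and the achieved 86.22% is disclosed beside it. All of this stands. It does not rescue the label, because section 2 reserves a successful primary conclusion for the full rule.

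The severe VE matters most. Section 3.1 assumes none. The single moderate/severe VE in section 3.5.1 belongs to the burden-of-disease simulations, section 5.5.4.2 carries separate moderate and severe parameters, and section 3.5.2 considers 80% to 90% for medical intervention. With severe VE 80% and shares of 25% or 1/6, the gap to 86.2% is only about 1 to 2 points. A reader might infer that the chance of primary success at VE 60% simply is 51% to 76%. The documents do not support that without the condition that severe VE equals overall VE, and the low end also ignores the delayed analysis.

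The SAP did consider severe events: it speaks of a reasonable likelihood of 5 placebo cases and of modeling with the 5:1 to 17:1 ratios, and section 5.4.4 refers to a modeling and simulation report that is not shown. That report may hold a joint figure; the SAP does not. Finally, section 3 says these calculations were not updated, and the primary analysis is past. This limits the consequence to the accuracy of the stated operating characteristics.

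**Conclusion.** The point holds as a mislabelled and incomplete power statement. The values 86.22%, 96.6% and nearly 100% are correct single-endpoint SPRT rejection probabilities; they are not the probability of the primary success defined in section 2. If severe VE equals overall VE, the shortfall at VE 60% is about 10 points (86 − 76) at a severe share of 25% and about 34 points (86 − 52) at 1/18. At VE 65% it is about 7 points (97 − 90) and 33 points (97 − 64). A higher severe VE shrinks it to almost nothing at the larger shares, but at 1/18 about 25 points (86 − 61) remain at severe VE 80% without the delayed analysis, and about 6 to 20 points with it (86 − 80 and 86 − 66).

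A reader might infer that the co-primary structure is a large part of the loss. It is not; the endpoints are nested, and condition 2 accounts for nearly all of it. Nor does anything here show an error in the boundary, the TNE or the type I error. The sizes rest on the assumed severe VE, the severe share, the Day 15 to 28 share of events and the handling beyond 154 events.

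**What to change.** In section 3.1, label 86.2%, 96.6% and 99.6% as single-endpoint SPRT rejection probabilities and drop the term *overall study power*. Keep about 90% there only as the basis of the fixed single-look test that sets the TNE (90.8%). In sections 2 and 5.4.3, replace about 90% with 86.2% for the truncated SPRT.

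Add one table of the probability of meeting the full section 2 rule, by overall VE (60, 65, 70%), severe share (25%, 1/6, 1/18) and severe VE (equal to overall VE, and 80%). State the assumed share of Day 15 to 28 events, the handling beyond 154 events, and which reading of the 5-severe-case condition is used. If the modeling and simulation report already holds such a table, citing its figures in section 3.1 would do.

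The cost is wording and a short simulation. The stated figure becomes less favourable; conduct, boundaries and type I error do not change.

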3.2. Immunogenicity Subset (double-blind Phase)

All participants included in the Immunogenicity Subset (N=400) will be added randomly at each stage of the staggered enrollment. Healthy adults (Subset 1a, n=100) will be enrolled in Stage 1a, adults with comorbidities (Subset 1b, n=100) in Stage 1b, healthy elderly (Subset 2a, n=100) in Stage 2a, and elderly with comorbidities (Subset 2b, n=100) in Stage 2b, with approximately 100 participants per group. The interactive web response system (IWRS) will be used to achieve these numbers and a 1:1 ratio between Ad26.COV2.S and placebo assignment within each Subset.

For participants in the Immunogenicity Subset (ie, participants at sites with access to appropriate processing facilities), blood will be collected for analysis of humoral immune responses on Day 1 (pre-vaccination), Day 29, Day 71, 6 months, 1 year, 18 months, and 2 years after double-blind vaccination.

A sample size of 400 participants, is estimated to be sufficient to allow robust description of immune responses to Ad26.COV2.S vaccine. These numbers are expected to provide a robust

understanding of the magnitude and kinetics of the humoral response induced by the Ad26.COV2.S vaccine.

3.3. Immunogenicity Correlates (Correlates Subset)

Correlates will be assessed based on immune responses and transcriptome modifications measured in a random subcohort of vaccine recipients and in all vaccine recipients who experience a SARS-CoV-2 event (a primary endpoint or a secondary infection endpoint). Also, placebo participants will be included in this subset (placebo infected, seropositive [based on N-protein] non-infected and seronegative non-infected), if feasible. The goal of this case-cohort study is to assess correlates of risk of the primary endpoint and of SARS-CoV-2 infection (and potential other secondary endpoints) in the vaccine group by comparing vaccine-induced immune responses and transcriptome modifications associated with COVID-19.

Controls will be matched with cases from the same stage (age, comorbidities) and other co-factors as deemed appropriate. These will be detailed in the Correlates SAP.

3.4. Safety (Safety Subset)

Solicited and unsolicited AEs will be captured only in the Safety Subset, ie, approximately 6,000 participants (~3,000 from the active group, ~3,000 from the placebo group; and including at least 2,000 from the older age group [≥ 60 years of age] if feasible). Solicited AEs will be followed for 7 days, unsolicited AEs will be followed for 28 days.

3.5. Power calculations for other efficacy endpoints

3.5.1. Burden of disease endpoint

The statistical power associated with the BOD endpoint was evaluated under a range of scenarios for VE_{mild} (30-50%) with $VE_{mod/sev}=60\%$ and a relative incidence of mild events equal to 20%. The power values for the null hypothesis of $VE=0\%$ under these scenarios were all greater than 99% for the BOD endpoint (conditional on clearing the primary endpoint test and adjusted for multiplicity).

Table 2 below presents the simulation-derived Type I error rates for $H_0: VE_{BOD} = 0\%$ and $H_0: VE_{BOD} = 30\%$, (the latter included to match the null for the primary endpoint), assuming a relative incidence of mild infections of 20% and vaccine efficacy for moderate or severe/critical infections $VE_{mod/sev}$. Both controlled (using a Pocock boundary) and uncontrolled (passing down full alpha = 2.5% one-sided) values are reported.

The values of VE_{mild} in **Table 2** are chosen to produce the required values of VE_{BOD} under the null hypotheses of VE equal to 30% and 0% respectively for each successive pair or rows. The large negative values of VE_{mild} required under some of the scenarios would in all likelihood be detected in the supplementary analysis planned for mild infections alone. It can be seen from **Table 2** that the Type I error rate for the BOD secondary endpoint is well-controlled for both null hypotheses considered using a Pocock boundary based on a single interim analysis, but would be inflated if

an uncorrected one-sided alpha of 2.5% were used (though the inflation is relatively small, at most 1.4% for the scenarios considered).

Table 2 Type I error rates for BOD secondary endpoint tested at the time PA is triggered referring to H_0: [VE] _BOD=0% and H_0: [VE] _BOD=30%, using a 2.5% one-sided alpha (uncorrected) and a Pocock boundary. The relative incidences of mild and severe infections are both assumed to be 20%.

VE_{mod/sev}	H0:BOD	VE_{mild}	Pocock	Full alpha
30%	VE=30%	30%	0.016	0.018
	VE=0%	-150%	0.014	0.016
50%	VE=30%	-70%	0.021	0.036
	VE=0%	-250%	0.021	0.039
60%	VE=30%	-120%	0.016	0.031
	VE=0%	-300%	0.015	0.028
70%	VE=30%	-170%	0.012	0.025
	VE=0%	-350%	0.016	0.031

The simulations that produced the results in [Table 2](#) were carried out using an event-based simulation engine. We allocate each event in a trial between the vaccine and placebo arms of the trial, and between mild, moderate and severe infections, using the categorical distribution. We compare the cumulative sums of moderate and severe events to the boundary to determine when boundary crossing occurs. We calculate the appropriate alpha level for secondary endpoint testing at the time of boundary crossing using a Pocock two-stage design, implemented using the gsDesign R package. The information fraction used is the number of moderate and severe events at the time of boundary crossing divided by the TNE. We compute the test statistic for the burden of disease endpoint using the formulas in Mehrotra et al. 2020. We simulate 10,000 trials for each scenario.

